11.9 Safety Analysis

AEs will be classified using standard MedDRA terminology Version 18.1 or higher and summarized by treatment group. Summary tables comparing the type, date of onset, date of resolution, incidence, severity, relationship to the IP, outcome and action taken will be prepared by treatment group. Should sufficient data exist, AE frequencies will be compared among treatments using Fisher's exact test or a similar test.

Application site reactions (erythema, dryness, burning/stinging, erosion, edema, pain, itching) recorded at each visit will be compared among treatment groups. A descriptive analysis comparing the application site reactions for each treatment group will be created.

Concomitant medication use during the treatment period will be tabulated by subject.

Signs and symptoms of acne vulgaris will not be considered AEs, unless in the Investigator's opinion, they have increased in frequency and/or severity to such an extent that the Investigator/subject considers that it is in the subject's best interest to be dropped from continued participation in the study and given alternative therapy for their condition.

All subjects who received randomized IP will be included in the comparative safety analysis. The eCRF for the study can allow for reporting by Investigators of lesion worsening beyond Grade 4 with treatment. It is recommended that enrollment of acne vulgaris subjects not include subjects with nodulocystic acne. Subjects who worsen beyond Grade 4 will be described in the safety evaluation.

CONFIDENTIAL PROTOCOL

A Multi-Center, Double-Blind, Randomized, Vehicle-Controlled, Parallel-Group Study Comparing Tazarotene Cream 0.1% to TAZORAC[®] (tazarotene) Cream 0.1% and Both Active Treatments to a Vehicle Control in the Treatment of Acne Vulgaris

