2. OBJECTIVES

The objectives of this study are to:

1. Evaluate the therapeutic equivalence of the Test product, Tazarotene Cream 0.1% (Fougera Pharmaceuticals Inc.) to the Reference product, TAZORAC[®] (tazarotene) Cream 0.1% (Allergan, Inc.) in the treatment of acne vulgaris.
2. Demonstrate the superiority of the efficacy of the Test and Reference (active) products over that of the Placebo in the treatment of acne vulgaris.
3. Compare the safety of the Test, Reference and Placebo products in the treatment of acne vulgaris.

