8. STATISTICAL ANALYSIS METHODS

If not otherwise specified, statistical significance is defined as $p < 0.05$ and is two-tailed. Data will be summarized with respect to demographic and baseline characteristics, efficacy variables and safety variables.

For categorical variables, the number and percent of each category within a parameter will be calculated for non-missing data. For continuous variables with non-missing values, statistics will include number of observations, mean, standard deviation, median, minimum and maximum values.

All statistical analyses will be conducted using SAS[®], Version 9.4 or higher. Datasets will be prepared using headings from Clinical Data Interchange Consortium (CDISC) Study Data Tabulation Model (SDTM) implementation for human clinical trials and ADaM (Analysis Dataset Model).

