8.3.1 Adverse Events

All the adverse events (AEs) reported throughout the study will be coded and classified according to the MedDRA (Medical Dictionary for Regulatory Activities) coding dictionary (Version 18.1 or higher). Each adverse event is to be evaluated for date of start and end, seriousness, severity, relationship to the IP, action taken and outcome.

In each of the following categories, the total number and percentage of subjects with 1) at least one AE, 2) discontinued study drug due to AEs, 3) AE severity and AEs related to the IP, 4) serious AEs and death will be summarized separately by treatment groups.

A summary table of the number and percent of subjects with AEs by system organ class, preferred term, and treatment group will be presented. Each patient will be counted only once within each preferred term.

[REDACTED]

STATISTICAL ANALYSIS PLAN

Tazarotene Cream 0.1%

Protocol / [REDACTED] 0454-01-01/[REDACTED]

A frequency summary table of the number of AEs by system organ class, preferred term, severity, and treatment group will be presented. Severity will be classified as “Mild”, “Moderate”, or “Severe”.

Similarly, a frequency summary table of the number of AEs by system organ class, preferred term, and relationship to the IP, and treatment group will be presented. Relationship to a study drug will be classified as “Suspected” or “Not Suspected”.

Should sufficient data exist, adverse event frequencies will be compared between treatments using Fisher’s exact test.

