9. TABLE, LISTING AND FIGURE SHELLS

The following shells are provided in order to provide a framework for the display of data from this study. These shells may not be reflective of every aspect of this study but are intended to show the general layout of the Tables, Listings and Figures that will be included in the final clinical study report. Tables, Listings and Figures are numbered following the ICH structure. Table headers, variables names and footnotes will be modified as needed following data analyses. All descriptive and inferential statistical analyses will be performed using SAS[®] statistical software Version 9.4 or higher, unless otherwise noted.

TABLE, LISTING AND FIGURE SHELLS

**T16.1.9.1 Summary of Discontinued Subjects
(Safety Population)**

Subjects	Test	Reference	Placebo	Total
Randomized	xxx	xxx	xxx	xxx
Completed Study	xxx	xxx	xxx	xxx
Terminated Early	xxx	xxx	xxx	xxx
Early Termination Reason				
Administrative reasons	xxx	xxx	xxx	xxx
Lack of efficacy	xxx	xxx	xxx	xxx
Lost to Follow-Up	xxx	xxx	xxx	xxx
etc.				

Test: Tazarotene Cream 0.1% (Fougera Pharmaceuticals Inc.)
Reference: TAZORAC® (tazarotene) Cream, 0.1% (Allergan, Inc.)
Placebo: Placebo (vehicle) Cream (Fougera Pharmaceuticals Inc.)

**T16.1.9.2 Summary of Protocol Deviations
(Safety Population)**

	Test	Reference	Placebo	Total
Total Subjects with Protocol Deviations	xxx	xxx	xxx	xxx
Total Deviations	xxx	xxx	xxx	xxx
Lost to follow up	xxx	xxx	xxx	xxx
Outside visit window	xxx	xxx	xxx	xxx
Missed Visit	xxx	xxx	xxx	xxx
Restricted Medication	xxx	xxx	xxx	xxx
etc	xxx	xxx	xxx	xxx
Other	xxx	xxx	xxx	xxx

Test: Tazarotene Cream 0.1% (Fougera Pharmaceuticals Inc.)
Reference: TAZORAC® (tazarotene) Cream, 0.1% (Allergan, Inc.)
Placebo: Placebo (vehicle) Cream (Fougera Pharmaceuticals Inc.)

**T16.1.9.3.1 Summary of Subjects Excluded from Efficacy Analysis
(Population Determination)**

		Test	Reference	Placebo	Total
Randomized	Total	xxx	xxx	xxx	xxx
Safety Population	Total	xxx	xxx	xxx	xxx
Excluded from Safety	Did not received study product etc.	xxx	xxx	xxx	xxx
mITT Population	Total	xxx	xxx	xxx	xxx
Excluded from mITT	Did not received study product etc.	xxx	xxx	xxx	xxx
PP Population	Total	xxx	xxx	xxx	xxx
Excluded from Excluded from PP	Restricted Medication etc.	xxx	xxx	xxx	xxx

Test: Tazarotene Cream 0.1% (Fougera Pharmaceuticals Inc.)
Reference: TAZORAC® (tazarotene) Cream, 0.1% (Allergan, Inc.)
Placebo: Placebo (vehicle) Cream (Fougera Pharmaceuticals Inc.)

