Test	xxx	xxx	xx.x%		
Reference	xxx	xxx	xx.x%	xx.x%	xx.x – xx.x

Superiority: modified Intent-to-Treat Population

Treatment Group	Number of Subjects (N)	Number of Treatment Successes (n)	Proportion of Treatment Successes (%)	P-value
Placebo	xxx	xxx	xx.x%	
Test	xxx	xxx	xx.x%	x.xxxx
Reference	xxx	xxx	xx.x%	x.xxxx

The 90% confidence interval for the difference in proportions between test and reference was calculated using Yates' correction.

Superiority of Active treatments over Placebo were tested using a two-sided Cochran-Mantel-Haenszel (CMH) exact test, stratified by clinical site, at the 5% significance level using last observation carried forward (LOCF).

Test: Tazarotene Cream 0.1% (Fougera Pharmaceuticals Inc.)
Reference: TAZORAC® (tazarotene) Cream, 0.1% (Allergan, Inc.)
Placebo: Placebo (vehicle) Cream (Fougera Pharmaceuticals Inc.)

**T16.1.9.12 Overall Summary of Adverse Events
(Safety Population)**

Description	Test N (%)	Reference N (%)	Placebo N (%)	Total N (%)
Subjects Randomized	xxx	xxx	xxx	xxx
Subjects with at least one AE	xx (xx.x%)	xx (xx.x%)	xx (xx.x%)	xx (xx.x%)
Discontinued study drug due to above AE	xx (xx.x%)	xx (xx.x%)	xx (xx.x%)	xx (xx.x%)
AEs reported	xxx	xxx	xxx	xxx
Mild	xx (xx.x%)	xx (xx.x%)	xx (xx.x%)	xx (xx.x%)
Moderate	xx (xx.x%)	xx (xx.x%)	xx (xx.x%)	xx (xx.x%)
Severe	xx (xx.x%)	xx (xx.x%)	xx (xx.x%)	xx (xx.x%)
Not Suspected	xx (xx.x%)	xx (xx.x%)	xx (xx.x%)	xx (xx.x%)
Suspected	xx (xx.x%)	xx (xx.x%)	xx (xx.x%)	xx (xx.x%)
Death	xx (xx.x%)	xx (xx.x%)	xx (xx.x%)	xx (xx.x%)
Serious AE	xx (xx.x%)	xx (xx.x%)	xx (xx.x%)	xx (xx.x%)

Test: Tazarotene Cream 0.1% (Fougera Pharmaceuticals Inc.)
Reference: TAZORAC® (tazarotene) Cream, 0.1% (Allergan, Inc.)
Placebo: Placebo (vehicle) Cream (Fougera Pharmaceuticals Inc.)

**T16.1.9.13 Summary of Frequency of All Adverse Events by Body System
(Safety Population)**

Body System	MedDRA Term	Test (N = xxx)		Reference (N = xxx)		Placebo (N = xxx)		Fisher's P-value
		Events	Subjects	Events	Subjects	Events	Subjects	
Patient with at least one AE	Total	Xx	xx (xx.x%)	xx	xx (xx.x%)	xx	xx (xx.x%)	x.xxxx
Ear and labyrinth disorders	Ear pain	Xx	xx (xx.x%)	xx	xx (xx.x%)	xx	xx (xx.x%)	x.xxxx
	etc.							
	etc.							

Comparison of treatment groups is with respect to the number of subjects with at least one occurrence of the AE.

Test: Tazarotene Cream 0.1% (Fougera Pharmaceuticals Inc.)
Reference: TAZORAC® (tazarotene) Cream, 0.1% (Allergan, Inc.)

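### The adverse event comparison names no contrast, its one-p-value shell implies a three-arm Fisher test, and no Test-minus-Reference estimate with an interval is planned

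*SAP*

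**What the plan says.** The third study objective (SAP section 2, same wording in protocol section 9) is to "Compare the safety of the Test, Reference and Placebo products in the treatment of acne vulgaris".

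For adverse events (AEs), SAP 8.3.1 gives one inferential method: if there are enough data, "adverse event frequencies will be compared between treatments using" Fisher's exact test. Protocol 11.9 says that "AE frequencies will be compared among treatments using" Fisher's exact test or a comparable alternative. Neither sentence states whether one test spans all three arms or whether pairs of arms are tested.

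Shell T16.1.9.13 in SAP section 9 has event and subject columns for Test, Reference and Placebo, then one column headed "Fisher's P-value". Its footnote reads: "Comparison of treatment groups is with respect to the number of subjects with at least one occurrence of the AE". T16.1.9.14, for AEs in at least 5% of subjects, is listed without a layout of its own. The introduction to the shells warns: "These shells may not be reflective of every aspect of this study".

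No AE text or shell contains a Test-minus-Reference difference, a confidence interval or a pairwise p-value. For efficacy, by contrast, T16.1.9.8.1, T16.1.9.10.1 and T16.1.9.11 each report a Test/Reference contrast with a 90% interval. SAP 8.4 states that no multiplicity adjustment is made.

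**The concern.** Protocol 8.5 expects drug-related effects to be more frequent in both active arms than under Placebo, mainly at the application site. For a term with that pattern, the hypothesis that all three arms share one rate is false even when Test and Reference behave identically. A small three-arm p-value then says that some arm differs, not that the generic differs from the Reference product. The reverse can also occur: a Test excess over Reference may be diluted when Placebo sits close to Reference.

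At stake is how the comparative safety objective is reported. A reader of T16.1.9.13 could take a significant p-value as a safety difference between the two creams, or a non-significant one as reassurance, when it establishes neither. Because the contrast is unstated and shell headers and footnotes may be changed after the data are analysed, it could also be settled with the results in view.

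**Working it through.** **Inputs from the documents**
- Planned arms: 1110 × 2/5 = 444 Test, 444 Reference; 1110 × 1/5 = 222 Placebo. This reproduces the split in SAP section 5 and is used here as the safety population.
- Significance level: 0.05, two-sided (SAP section 8: "If not otherwise specified, statistical significance is defined as" p below 0.05, two-tailed).
- Direction only: more drug-related risk in both active arms (protocol 8.5).

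**Assumed:** AE rates, since the documents give none. All rates below are ordered Test/Reference/Placebo.

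**Three-arm Fisher test.** With m = a + b + c subjects having the event, the table probability is C(444,a) × C(444,b) × C(222,c) / C(1110,m). The p-value sums the probabilities of all tables no more likely than the one observed. The Test versus Reference p-value is the ordinary 2×2 Fisher test.

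**Worked tables**
- 60/60/10 subjects (13.5/13.5/4.5%): three-arm p = 0.0003, Test versus Reference p = 1.0. The difference is 0 with a Wald 95% half-width of 1.96 × √(2 × 0.135 × 0.865 / 444) = 0.045, that is −4.5 to +4.5 points.
- 53/34/17 subjects (11.9/7.7/7.7%): three-arm p = 0.064, Test versus Reference p = 0.042. Difference 0.0428; half-width 1.96 × √(0.1194 × 0.8806/444 + 0.0766 × 0.9234/444) = 0.0390; 95% CI 0.4 to 8.2 points. Newcombe's interval is also 0.4 to 8.2.

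**Simulation** (at least 1,500 trials per scenario; Monte Carlo standard error at most √(0.25/1500) = 1.3 points)

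Active arms truly equal and clearly above vehicle:

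| Rates | Three-arm p < 0.05 | Of those, Test vs Reference p < 0.05 |
|---|---|---|
| 10/10/5% | about 60% | about 6% |
| 5/5/1% | 81% | 4.5% |
| 12/12/4% | about 96% | about 4% |
| 15/15/5% | about 99% | about 4% |

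Active arms equal and only slightly above vehicle, or events rare: the three-arm test is significant in about 11 to 13% (10/10/8%), 17% (5/5/3%), 27% (3/3/1%) and 10% (2/2/1%) of trials.

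Test truly worse than Reference:
- Vehicle low (15/10/2%): the three-arm test is significant in about 100% of trials, Test versus Reference in about 57%. The three-arm result looks much as it does at 15/15/5%.
- Vehicle equal to Reference (15/10/10, 10/6/6, 5/2/2%): 86 to 89% of significant three-arm results also have Test versus Reference p < 0.05. In a further 4 to 6% of trials only the pairwise test is significant.
- 11/6/8%: three-arm 66.5%, pairwise 72.0%, pairwise only about 8%.

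**Precision of the missing estimate.** With equal rates p, the 95% half-width is 1.96 × √(2p(1 − p)/444): 2.9 points at 5%, 3.9 at 10%, 5.3 at 20%.

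**The case against.** Four points on the other side carry weight.

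- A reader might infer that the SAP commits to a three-arm test. It does not say so. That reading rests on the layout of a shell declared to be a framework, and on the protocol's word *among*. What can be shown is that the contrast is unspecified.
- A reader might also infer that a significant p-value will mostly reflect retinoid versus vehicle. That depends on rates the documents do not give. It holds for terms with a marked class effect. It fails where vehicle resembles Reference, and the rejection rate is low where the excess over vehicle is small. Some expected local effects may also never enter the AE table: application site reactions are graded at every visit and summarised separately in T16.1.9.18 and T16.1.9.19, and a change becomes an AE only if the Investigator judges it so (protocol 10.7). Those tables carry no test and no difference either, so they do not supply the missing estimate.
- It would be too strong to say the plan cannot address Test versus Reference. T16.1.9.13 shows events, subjects and percentages by arm, so the difference can be formed by hand. Objective 3 names all three products, and a three-group test fits that wording. What is absent is a stated contrast and a measure of precision.
- The loss from masking is modest: 72.0 − 66.5 = 5.5 points of power at 11/6/8%, and the 53/34/17 table was picked to straddle 0.05.

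Testing is also conditional on sufficient data, and no decision rule uses it.

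**Conclusion.** The point holds as a gap in specification and reporting. SAP 8.3.1 names no contrast, the shell most naturally implies one three-arm p-value per term, and no AE output gives a Test-minus-Reference difference with its precision, although comparative safety is an objective.

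Its size depends on the term. With equal active arms, the three-arm p-value falls below 0.05 in roughly 60 to 96% of trials at assumed rates of 10/10/5% to 12/12/4%, but in under one trial in five at 10/10/8% or 5/5/3%. These figures rest on assumed rates, on all 1110 subjects being in the safety population, and on the three-arm reading of the shell.

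The equivalence and superiority conclusions are untouched: both rest only on the co-primary lesion-count endpoints. This is an inexpensive improvement to safety reporting, not a threat to the trial's main result.

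**What to change.** In SAP 8.3.1 and shells T16.1.9.13 and T16.1.9.14:

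1. Add the Test-minus-Reference difference in subject incidence with a 95% confidence interval (Newcombe or exact) for any AE and for preferred terms, at least those occurring in 5% or more of subjects.
2. Label any Fisher p-value that is kept with the arms it compares.
3. State that these differences, intervals and p-values are descriptive, since SAP 8.4 makes no multiplicity adjustment.

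The interval is the essential part. Pairwise p-values are optional, and a non-significant one would not show comparable safety. Protocol 11.9 need not be amended, because it already allows an alternative to Fisher's test.

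The cost is SAP wording and a few table columns, with no new data. The downside is more unadjusted intervals, some of which will exclude zero by chance.

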8.3.2 Application Site Reactions

At Visits 1, 2, 3 and 4 the Investigator will evaluate the patient for local application site reactions based on the scale provided in Appendix B:

Signs and Symptoms recorded at each visit will be compared between treatment groups. Descriptive summaries (number of observations, mean, standard deviation, minimum, median and maximum) comparing the application site reactions for each treatment group will be presented by visit.

A frequency summary table comparing the application site reactions for each treatment group will be presented by visit.

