10.3.5 Early Termination

If a subject terminates from the study early, all efforts will be made to complete Visit 4 study procedures, obtain any outstanding data and collect all IP. In case of early termination, the Investigator shall fully document the reason for early termination and the date of removal.

In the event that a subject discontinues from the study at any time due to an AE, the reason for discontinuation, the nature of the event and its clinical course must be fully documented. For such a subject, the Investigator should follow the subject until the AE has resolved, has become clinically insignificant, is stabilized, is confirmed to be ongoing at the end of the study or the subject is lost to follow-up. Should a serious adverse event (SAE) be noted, procedures stated in section 10.7.4 must be followed. Should pregnancy be noted, procedures stated in section 10.7.6 must be followed.

Subjects who discontinue early because of lack of treatment effect after completing four weeks of treatment will be included in the Per-Protocol (PP) population as treatment failures provided they had no significant protocol deviations (PDs). Any PD that would compromise the integrity of the data will be considered significant.

Subjects who discontinue early due to a worsening condition and require alternate or supplemental therapy for the treatment of acne during the study should be discontinued, included in the PP population analysis as treatment failures (provided they had no significant PDs during their time of study participation), and referred for effective treatment outside of the study.

Subjects who discontinue early for reasons besides lack of treatment effect or worsening of condition should be excluded from the PP population, but included in the modified Intent-to-Treat (mITT) population using the last observation carried forward (LOCF), provided they administered at least one dose of randomized IP and completed at least one post-dose evaluation.

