5. **Lesion Count:** A validated/qualified staff will perform count of inflammatory lesions (i.e., papules and pustules), non-inflammatory lesions (i.e., open and closed comedones) and nodulocystic lesions (i.e., nodules and cysts).
6. **Application Site Reactions:** A Medical Investigator will evaluate any Application Site Reactions since the last visit. See Appendix B.
7. **Collect and Review Subject's Diary:** Collect the diary from the subject and review for compliance with the protocol requirements.
8. **IP Collection:** Collect all used and unused tubes and return them to their corresponding kit box(s) for storage. Record any lost or significantly damaged (i.e., punctured) IP.
9. **Discharge from Study:** Discharge the subject from the study.

CONFIDENTIAL PROTOCOL

A Multi-Center, Double-Blind, Randomized, Vehicle-Controlled, Parallel-Group Study Comparing Tazarotene Cream 0.1% to TAZORAC® (tazarotene) Cream 0.1% and Both Active Treatments to a Vehicle Control in the Treatment of Acne Vulgaris

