10.6.9 Application Site Reactions

At Visit 1, the Investigator will grade the individual signs and symptoms per Appendix B. This will serve as a baseline for subsequent assessments of application site reactions. At Visits 2, 3 and 4, the Medical Investigator will evaluate the subject for local application site reactions (erythema, dryness, burning/stinging, erosion, edema, pain, and itching) based on the scale provided in Appendix B. Reactions will be documented in source documents for each subject.

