PROCEDURE	VISIT 1 (Day -14 to 1) Screening/ Baseline	VISIT 2 (Day 28 ± 4 Days) Interim Visit	VISIT 3 (Day 56 ± 4 Days) Interim Visit	VISIT 4 (Day 85 ± 4 Days)* End of Study/ Early Termination
Informed Consent/Assent	X [‡]			
Medical History/ Demographics	X [‡]			
Pregnancy Test [†]	X [‡]	X	X	X
Vital Signs	X [‡]			X
Lesion Counts	X [‡]	X	X	X
Investigator's Global Assessment	X [‡]	X	X	X
Application Site Reactions	X	X	X	X
Inclusion/Exclusion Criteria Review	X [‡]			
Concomitant Medication	X [‡]	X	X	X
Randomization	X			
Dispense IP	X	X**	X**	
Return of IP		X**	X**	X
Dispense Subject Diary /Supplies	X	X	X	
Collect/Review Subject Diary		X	X	X
Adverse Events		X	X	X
Discharge from Study				X

* Dosing regimen is once daily in the evening through the evening for 84 days (Day 1 to Day 84) before Visit 4 (Day 85 ± 4)

** If applicable, based on use of previously dispensed product.

† For females of childbearing potential

‡ Procedures performed as part of the screening assessment, before randomization

[REDACTED]

STATISTICAL ANALYSIS PLAN

Tazarotene Cream 0.1%

Protocol / [REDACTED] 0454-01-01/[REDACTED]

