**T16.1.9.18 Summary of Application Site Reaction
 (Safety Population)**

Signs and Symptoms	Visit	Statistic	Test (N = xxx)	Reference (N = xxx)	Placebo (N = xxx)
Erythema	1	n	xxx	xxx	xxx
		Mean ± SD	xx.x ± xx.x	xx.x ± xx.x	xx.x ± xx.x
		Median	xx.x	xx.x	xx.x
		Range	xx.x – xx.x	xx.x – xx.x	xx.x – xx.x
	2				
	3				
	4/ET				
Dryness					
Burning/Stinging					
Erosion					
Edema					
Pain					
Itching					

Test: Tazarotene Cream 0.1% (Fougera Pharmaceuticals Inc.)
 Reference: TAZORAC® (tazarotene) Cream, 0.1% (Allergan, Inc.)
 Placebo: Placebo (vehicle) Cream (Fougera Pharmaceuticals Inc.)

**T16.1.9.19 Summary of Frequency of Application Site Reaction
 (Safety Population)**

Signs and Symptoms	Visit	Statistic	Test (N = xxx)	Reference (N = xxx)	Placebo (N = xxx)	
Erythema	1	Absent	xxx (xx.x%)	xxx (xx.x%)	xxx (xx.x%)	
		Mild	xxx (xx.x%)	xxx (xx.x%)	xxx (xx.x%)	
		Moderate	xxx (xx.x%)	xxx (xx.x%)	xxx (xx.x%)	
		Severe	xxx (xx.x%)	xxx (xx.x%)	xxx (xx.x%)	
	2	3	4/ET			
	Dryness	Burning/Stinging	Erosion	Edema	Pain	Itching

Test: Tazarotene Cream 0.1% (Fougera Pharmaceuticals Inc.)
 Reference: TAZORAC® (tazarotene) Cream, 0.1% (Allergan, Inc.)
 Placebo: Placebo (vehicle) Cream (Fougera Pharmaceuticals Inc.)

**T16.1.9.20 Summary of Vital Signs
 (Safety Population)**

Vital Signs	Visit	Statistic	Test (N = xxx)	Reference (N = xxx)	Placebo (N = xxx)
Systolic Blood Pressure (mmHg)	1	n	xxx	xxx	xxx
		Mean ± SD	xxx.x ± xx.x	xxx.x ± xx.x	xxx.x ± xx.x
		Median	xxx.x	xxx.x	xxx.x
		Range	xx.x – xx.x	xx.x – xx.x	xx.x – xx.x
	4/ET				

Diastolic Blood Pressure (mmHg)
 Pulse Rate (beats/min)
 Respiration Rate (breaths/min)
 Temperature (F)

Test: Tazarotene Cream 0.1% (Fougera Pharmaceuticals Inc.)
 Reference: TAZORAC® (tazarotene) Cream, 0.1% (Allergan, Inc.)
 Placebo: Placebo (vehicle) Cream (Fougera Pharmaceuticals Inc.)

L16.2.1 Listing of Discontinued Subjects

Treatment Group	Patient Number	Discontinuation Reason	Population
Test	xx - xxxx	Withdrew Consent	Safety
	xx - xxxx	Lost to Follow-up	Safety
Reference			
Placebo			

Test: Tazarotene Cream 0.1% (Fougera Pharmaceuticals Inc.)
Reference: TAZORAC® (tazarotene) Cream, 0.1% (Allergan, Inc.)
Placebo: Placebo (vehicle) Cream (Fougera Pharmaceuticals Inc.)

L16.2.2 Listing of Protocol Deviations

Treatment Group	Patient Number	Protocol Deviation Summary	Population
Test	xx - xxxx	Outside Visit Window	Safety

Reference

Placebo

Test: Tazarotene Cream 0.1% (Fougera Pharmaceuticals Inc.)

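### Application site reactions are tabulated only by visit, so no table shows how many subjects were ever affected, and pooling Early Termination with Visit 4 mislabels timing

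*SAP*

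**What the plan says.** SAP 8.3.2 plans two outputs for the graded signs, both organised by visit. Descriptive summaries (n, mean, SD, minimum, median, maximum) "comparing the application site reactions for each treatment group will be presented by visit". For the counts: "A frequency summary table comparing the application site reactions for each treatment group will be presented by visit". The comparison between arms is framed the same way: "Signs and Symptoms recorded at each visit will be compared between treatment groups". No test and no per-subject measure is named.

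In SAP 9, the shell "T16.1.9.18 Summary of Application Site Reaction" and its companion T16.1.9.19 have rows 1, 2, 3 and 4/ET. Neither they nor the SAP's table list include a worst-grade summary, an ever-affected count, a shift from Visit 1 or a separate ET row.

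Protocol 10.6.9 says of the Visit 1 grading: "This will serve as a baseline for subsequent assessments of application site reactions".

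The schematic in SAP 3 gives early leavers the same column as completers: "VISIT 4 (Day 85 ± 4 Days)* End of Study/ Early Termination". Protocol 10.3.5 adds: "If a subject terminates from the study early, all efforts will be made to complete Visit 4 study procedures". An ET assessment can therefore fall on any study day.

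The instructions for Visits 2, 3 and 4 (Protocol 10.5.2 to 10.5.4) include a look-back: "A Medical Investigator will evaluate any Application Site Reactions since the last visit".

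**The concern.** Objective 3 is to compare the safety of the three products, and Protocol 8.5 expects tazarotene's effects mainly at the application site. The natural tolerability measure is how many subjects in each arm ever had a given reaction, how bad it became, and whether it was worse than at entry. By-visit rows do not give this, because they do not link one subject's visits.

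The second problem is timing. A subject who leaves in week 2 with a reaction is absent from the Visit 2 and 3 rows and appears in a row that otherwise holds grades from Day 85 ± 4. A reader of that row cannot separate early intolerance from reactions still present after 12 weeks.

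**Working it through.** There is no planned figure to reproduce, since the documents state no reaction rates. The rates below are assumptions. The arm size comes from SAP 5: 1110 × 2/5 = 444 per active arm.

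**A. By-visit rows against the share ever affected.** Let p₂, p₃ and p₄ be the proportions with a given grade or worse at the three post-baseline visits, with all 444 subjects assessed each time. The rows fix only these three numbers. The share ever affected lies between max(p) and min(1, p₂ + p₃ + p₄), and equals 1 − (1 − p₂)(1 − p₃)(1 − p₄) if visits are independent.

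| Each row shows | Lower bound | Upper bound | Independent visits |
|---|---|---|---|
| 5% | 5% | 15% | 14.3% |
| 10% | 10% | 30% | 27.1% |
| 20% | 20% | 60% | 48.8% |

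For the 10% case, independence gives 1 − 0.9³ = 0.271. If a subject's visits are positively correlated (latent normal model), the share is 24.2%, 21.8% and 17.2% at correlations 0.3, 0.5 and 0.8. In subjects, 44 of 444 are affected in each row, while those ever affected number about 120 (independent), 107, 97 or 76. The lower bound is reached when the same subjects react every time.

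**B. Pooling ET with Visit 4.** Assume k of 444 subjects leave before Visit 2 with grade 3 and all have an ET assessment. Among the 444 − k who continue, 2% have grade 3 at Visit 2 and 1% at Week 12, and nobody else leaves. Percentages are of subjects assessed, following the non-missing rule in SAP 8.

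- Visit 2 row as shelled: 0.02(444 − k)/(444 − k) = 2.0% for every k
- Visit 2 by actual timing: [0.02(444 − k) + k]/444
- 4/ET row as shelled: [0.01(444 − k) + k]/444
- Week 12 attenders alone: 1.0%

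For k = 20, 424 continue. Visit 2 by actual timing is (8.48 + 20)/444 = 6.4%, and the 4/ET row is (4.24 + 20)/444 = 5.5%.

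| k | Visit 2 as shelled | Visit 2 by timing | 4/ET as shelled | Week 12 attenders |
|---|---|---|---|---|
| 5 | 2.0% | 3.1% | 2.1% | 1.0% |
| 10 | 2.0% | 4.2% | 3.2% | 1.0% |
| 20 | 2.0% | 6.4% | 5.5% | 1.0% |
| 40 | 2.0% | 10.8% | 9.9% | 1.0% |

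The k subjects are counted in every case, but in the wrong row for when they reacted.

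**The case against.** The SAP does what the protocol asks. Protocol 11.9 calls only for a descriptive comparison of reactions recorded at each visit, and SAP 9 says the shells may not reflect every aspect of the study. That stands: the two documents agree, and the missing summary is a gap in both.

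There are also backstops. The look-back means a reaction that resolves between visits can still be graded, although it does not link visits within a subject. For AEs, T16.1.9.13 counts affected subjects by term over the whole study with a Fisher p-value. T16.1.9.12 counts those who stopped because of an AE, T16.1.9.1 gives reasons for early termination, and L16.2.7.1 gives dates and severity. These are strongest where a reaction led to stopping. They are incomplete because Protocol 10.7 leaves it to the Investigator whether a changed reaction is reported as an AE, and because T16.1.9.15 shows severity by events rather than by subjects.

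A reader might infer three stronger things that the documents do not support:

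- **Pooling ET hides reactions.** It does not. T16.1.9.19 gives counts by grade, so early leavers' grades remain in the 4/ET row. The effect is on timing.
- **The tables would mask a Test–Reference difference.** The calculations concern a single arm under assumed rates and say nothing about differential masking.
- **The Visit 1 grade is not used at all.** Both shells print it by arm beside later visits. What is missing is the within-subject change.

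**Conclusion.** The point holds as a modest gap in safety reporting. With by-visit rows only, any single row can understate the share of subjects ever affected, by a factor of up to three when the three rows are equal (10% shown, up to 30% ever affected). The actual size cannot be known from the documents, and it is nil if the same subjects react at every visit and none leaves early. The understatement rests on the missing any-time and worst-grade summary.

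Pooling ET with Visit 4 is a separate, smaller fault of labelling: it lowers the Visit 2 and 3 rows and raises the last row by an amount that depends on how many leave early with reactions. The co-primary equivalence and superiority analyses are unaffected.

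**What to change.** In SAP 8.3.2, add one table by arm on the Safety population. For each of the seven signs, give the number and percent of subjects by worst post-baseline grade and by worst increase from the Visit 1 grade. Use Visits 2, 3, 4 and ET, plus any grade that happens to have been recorded at an unscheduled visit. The schedule plans no reaction assessment at such visits, so none should be assumed. State the denominator.

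In T16.1.9.18 and T16.1.9.19, show ET in its own row, apart from Visit 4 (Day 85 ± 4).

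The cost is one extra table and one extra row per sign in the two existing shells, all from data already collected.
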